 5. Initial diagnosis of AKI established either upon presentation to medical care at the study site in those patients with suspected or confirmed abdominal infection or surgically confirmed NSTI; or in those patients in whom the initial diagnosis of AKI is established during the 48-hour period from the suspected or confirmed diagnosis of abdominal infection or surgical confirmation of NSTI.

AKI Stage 2 or 3 according to the following KDIGO AKI criteria:

a. Stage 2 AKI

- i. Increase in serum creatinine to $\geq 200\%$ (≥ 2.0 -fold) from a reference creatinine value (see below) in the absence of primary underlying renal disease (eGFR >30 mL/min)

OR

- ii. Urine output < 0.5 mL/kg/hr x 12 hours following adequate fluid resuscitation [the aggregate over any 12-hour period can be used with hourly rate being relatively persistent over the 12-hour period]

Urine output should be calculated using Ideal Body Weight (IBW; using the Miller Formula⁵²)

b. Stage 3 AKI

- i. Increase in serum creatinine to $\geq 300\%$ (≥ 3.0 -fold) from a reference creatinine value in the absence of primary underlying renal disease (eGFR >30 mL/min)

OR

- ii. Serum creatinine ≥ 4 mg/dL

OR

- iii. Planned or initiation of RRT for acute AKI

- Order for RRT must be in place
- RRT may be started prior to study drug administration as long as the patient is off RRT during study drug administration and up to at least one hour post study drug administration

OR

- iv. Urine output < 0.3 mL/kg/hr x 24 hours or anuria x 12 hours following adequate fluid resuscitation
 - Urine output should be calculated using IBW (using the Miller Formula)

The reference creatinine value is the serum creatinine value according to the following order:

- i. Value within 3 months of the hospital admission
 - If single value available, then use the single value for reference
 - If two values available, then use the average of two values for reference
 - If three or more values available, then use the median of the three most recent values for reference
 - ii. Value between 3 and 12 months prior to hospital admission
 - If single value available, then use the single value for reference
 - If two values available, then use the average of two values for reference
 - If three or more values available, then use the median of the three most recent values for reference
 - iii. At hospital admission (if the patient is admitted without an acute illness)

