- c. Patients without a reference creatinine value would also be considered to have Stage 2 or 3 AKI if they have a serum creatinine $\geq 200\%$ (≥ 2.0 -fold) the normal creatinine value for age, race, and gender (Appendix F) and a renal ultrasound (US) or computed tomography (CT) showing normal kidney size within the past 90 days. Normal kidney size is defined as
- i. Computed Tomographic Scan
 - ii. If either kidney is ≥ 9 cm length
 - iii. Renal Ultrasound⁵⁴
 - <60 years if either kidney is ≥ 10 cm length
 - ≥ 60 years if either kidney is ≥ 9.5 cm length
6. Study medication must be administered within 6 hours of confirmation of onset of Stage 2 or 3 AKI as established at the study site, under the following criteria
- After the decision is made by the attending surgeon at the study site for a surgical or interventional radiology procedure for the abdominal infection

OR

- After confirmed diagnosis of abdominal infection has been established by a surgical or interventional radiology procedure
- OR
- After surgical confirmation of NSTI
7. Females of childbearing potential must consistently use an acceptable method of contraception from baseline through Day 28. Females of childbearing potential must have a negative β -subunit hCG pregnancy test (urine or blood whichever is faster; blood only in France) immediately prior to study entry.
 - Non-childbearing potential is defined as current tubal ligation, hysterectomy, or ovariectomy or post-menopause (1 year without menses with an appropriate clinical profile at the appropriate age e.g. >45 years).
 - Acceptable methods of contraception for this study is defined as abstinence, hormonal therapy (e.g., oral contraceptives, hormone implants), intra-uterine (IUD) device, diaphragm with spermicide, condom with spermicide.
 8. If a male patient's sexual partner is of childbearing potential, the male patient must acknowledge that they will consistently use an acceptable method of contraception (defined above) from baseline through Day 28.

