 - Full chemistry panel (see Section 9.2.11)
 - Complete blood count (CBC) with differential and platelet count
- Spot urine for albumin to creatinine ratio
- Standard C-reactive protein (CRP)

- Arterial blood gas and FiO₂ (if applicable) or SpO₂ and FiO₂ if arterial blood gas is not clinically indicated
- Blood culture for both aerobic and anaerobic bacteria
- Pregnancy test if applicable (blood or urine whichever is faster; blood only in France)
- Screening SOFA score will include measurements must be performed prior to study drug administration: SOFA score should be evaluated any time after arrival at the hospital (may include data from referring hospital), although no more than 6 hours prior to study drug administration. Baseline SOFA score will include the following organ/systems (with the total score being at least a 2): respiratory, cardiovascular, renal, coagulation, GI/hepatic and CNS.
- APACHE II score (measurement for this score will be collected and the score will be calculated retrospectively) using the worst values within the 24-hour period prior to enrollment
- Critical care parameters (dates and times of assisted ventilation, vasopressor use, ICU and hospital admission and discharge)
- Collect data on acute RRT
- Record additional relevant procedures related to the kidney (e.g., renal biopsy)
- Record any imaging that evaluates the kidney
- Local lesion assessment and evidence of amputation (excision to a joint space) if NSTI
- During surgery, peritoneal or abscess fluid, abdominal tissue samples, or NSTI tissue samples for microbiology
- Collect blood for serum for storage (immunogenicity testing)
- Collect urine and blood for plasma for storage (AKI biomarker analysis) – optional sub-study
- Collect blood for systemic inflammatory biomarkers – leukocyte transcriptome (RNA expression) profiling and chemokines / cytokines – optional sub-study
- Record Survival
- Perform randomization and study drug preparation if patient has confirmed diagnosis of Stage 2 or 3 AKI
 - Patients with suspected or confirmed abdominal infection or surgically confirmed NSTI who do not meet AKI criteria at time of abdominal infection presentation or surgical confirmation of NSTI should be followed every 6 hours with a repeat creatinine test and monitoring of urine output every 1 to 6 hours, for up to 48 hours after the suspected diagnosis of abdominal infection or surgical confirmation of NSTI, to determine if they develop Stage 2 or 3 AKI

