- Upon study drug administration patient is transitioned to Visit 2 (Day 1)

Visit 2 (Day 1)

Starts only upon study drug administration and terminates at the end of the calendar day. For abdominal sepsis, study drug may be given prior to, during, or after surgery if meets

all criteria. For NSTI, study drug may only be given during surgery or immediately after surgery (after surgical confirmation of NSTI).

- Drug (to be infused over 10 minutes) should be administered within 6 hours, under the following criteria, whichever is later, (as described in inclusion criteria Section 6.1):

- After confirmation of Stage 2 or 3 AKI as established at the study site

AND

A. Abdominal Infection

- After the decision is made by the attending surgeon at the study site for a surgical or interventional radiology procedure for the abdominal infection

OR

- After confirmed diagnosis of abdominal infection has been established by a surgical or interventional radiology procedure

OR

B. Necrotizing Soft Tissue Infection

- After surgical confirmation of NSTI (drug should not be administered until surgical confirmation of NSTI is established)

Note: If a surgical or interventional radiology procedure for the abdominal infection, or surgical confirmation of NSTI, occurred at an outside hospital prior to transfer to the study site, study medication must be administered within 6 hours of re-established diagnosis of Stage 2 or 3 AKI at the study site.

- Record if overdose
- Record any follow-up surgical or interventional radiologic procedures for previously documented abdominal infection or NSTI
- Collection of AEs/ SAEs
- Concomitant medications
- Vital signs (first set of vitals on that day)
- Symptom-driven interim PE
- Fluid balance (total in/out-I/O) for calendar day starting from the time accurate I/Os recorded (start time may be prior to study drug administration)
- Detailed urine output
 - Should be recorded continuously from time of study drug administration to Day 7 (if still in ICU or step down unit), using most frequent hourly intervals available and by calendar day with or without Foley catheter in place
- Spot urine for albumin to creatinine ratio
- Collect data on acute RRT
- Record additional relevant procedures related to the kidney (e.g., renal biopsy)
- Record any imaging that evaluates the kidney
- Weight, only if not collected at screening
- Collect data on additional amputations if NSTI

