5.6 Subgroup Analysis

Subgroup analysis will be performed. The following variables will define subgroups.

⁴ Vincent JL, Moreno R, Takala J, et al: The SOFA (Sepsis-related Organ Failure Assessment) score to describe organ dysfunction failure: On behalf of the Working Group on Sepsis-Related Problems of the European Society of Intensive Care Medicine. *Intensive Care Med* 1996; 22:707–710.

⁵ Vincent JL, Angus DC, Artigas A, Kalis A, Basson BR, Jamal HH, Johnson III G., Bernard GR for the PROWESS Study Group. Effects of drotrecogin alfa (activated) on organ dysfunction in the PROWESS trial. *Crit Care Med* 2003; 31:834 – 840.

- Stage 2 and Stage 3 AKI
- Acuity of AKI (i.e., whether or not AKI is diagnosed at time of presentation of abdominal infection or surgically confirmed NSTI, or during the 48 hours from the suspected diagnosis of abdominal infection or surgical confirmation of NSTI; developed AKI up to <24 hours or 25 to 48 hours after the suspected diagnosis of abdominal infection or surgical confirmation of NSTI)
- AKI diagnosed via creatinine criteria vs. urine output criteria
- Abdominal infection or NSTI
- Age ≥ 18 to ≤ 75 and > 75 to ≤ 85 years old
- Baseline APACHE II ≥ 10 and < 10
- Cardiovascular failure yes and no
- Respiratory failure yes and no
- Gender male and female
- Causcasian and other
- BMI category (< 30 , 30-40, > 40)
- Day 14 mSOFA ≤ 1 and Day 14 mSOFA ≥ 2

The following tables will be provided for each subgroup. Results for the primary endpoint will be summarized in a forest plot.

14.2.1.1	Numbers and Percentages of Subjects Achieving Freedom from Durable Loss of Renal Function and Improvement in Durable Loss of Renal Function at Day 28 Using LOCF ITT Analysis Set
14.2.2.1	Numbers and Percentages of Subjects Achieving Secondary Freedom from or Improvement in Durable Loss of Renal Function Endpoints at Days 14, 28, and 90 ITT Analysis Set

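### One Visit 2 sentence ties NSTI dosing to the operation and, read literally, conflicts with the AKI-linked 6-hour window used elsewhere

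*Protocol*

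**What the plan says.** **The restrictive sentence.** The opening text of Visit 2 in Protocol 7.3 lets abdominal patients be dosed before, during or after surgery. It then adds: "For NSTI, study drug may only be given during surgery or immediately after surgery (after surgical confirmation of NSTI". The word *immediately* is not defined.

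**The AKI-linked rules.**
- Protocol 6.1, inclusion 5, accepts AKI first "established during the 48-hour period from the suspected or confirmed diagnosis of abdominal infection or surgical confirmation of NSTI".
- Protocol 7.3, Screening, has patients without AKI at that point followed every 6 hours "for up to 48 hours after the suspected diagnosis of abdominal infection or surgical confirmation of NSTI". The trigger for allocation is: "Perform randomization and study drug preparation if patient has confirmed diagnosis of Stage 2 or 3 AKI".
- Protocol 6.1, inclusion 6: "Study medication must be administered within 6 hours of confirmation of onset of Stage 2 or 3 AKI as established at the study site", provided NSTI has been surgically confirmed.
- The dosing list in Visit 2 gives 6 hours from the later of AKI confirmation and surgical confirmation.
- The Note below that list covers patients whose NSTI was confirmed at another hospital before transfer: "study medication must be administered within 6 hours of re-established diagnosis of Stage 2 or 3 AKI at the study site".
- Protocol 8.1 and 9.2.1 run the 6 hours from AKI diagnosis and set no limit relative to the end of surgery.
- SAP 7.6 says that patients who present with NSTI alone and are then followed for AKI are to be dosed within 6 hours of the AKI diagnosis.

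**Where the timing enters the analysis.** Acuity of AKI (at presentation or in the following 48 hours) is a stratification factor, and Protocol 4.5 and 12.6.1 name NSTI in its definition. SAP 5.6 and 8.8 plan a split by whether patients "developed AKI up to <24 hours or 25 to 48 hours after the suspected diagnosis of abdominal infection or surgical confirmation of NSTI".

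**The concern.** The plan recruits, follows and randomises NSTI patients with late AKI, stratifies on the lateness and plans a subgroup on it. One sentence in the dosing visit, taken at its word, then bars the drug for many of them. This is separate from the question of when the 6-hour clock starts: settling the clock would leave the sentence in force.

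At stake is consistency across up to 90 sites. Two sites with the same patient could act differently, and each could point to protocol text. That would affect who enters the trial, who is exposed to study drug, and what counts as a protocol deviation.

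**Working it through.** The check is mainly a comparison of texts. The plan gives no figure of its own on this point.

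**Step 1. Latest dosing time under the AKI-linked rules.**
- Latest AKI diagnosis after surgical confirmation of NSTI: 48 h (inclusion 5).
- Dosing window after AKI confirmation: 6 h (inclusion 6).
- Upper bound: 48 + 6 = 54 h after surgical confirmation.

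This is the extreme case, not a typical one.

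**Step 2. A case inside the window.** AKI is confirmed 30 h after surgical confirmation. Inclusion 6 permits dosing until 30 + 6 = 36 h. The Visit 2 sentence permits none, unless the patient is in a repeat operation, or has just left one, between 30 and 36 h.

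**Step 3. Is late AKI unusual by the plan's own criteria?** Stage 2 by urine output needs 12 hours of low output. A patient with normal output at surgery therefore cannot qualify by that route until about 12 h later. Creatinine is rechecked every 6 hours. Late confirmation is what the screening follow-up is set up to find.

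**Step 4. Transferred patients.** The Note gives 6 hours from re-established AKI diagnosis at the study site. A patient operated on elsewhere and then transferred may be well past the operation by then. The sentence and the Note can agree only if the transfer is very quick or there is further surgery.

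**Step 5. Is there an exemption?** The sections listed above contain none for late-AKI or transferred NSTI patients. Footnote t of Protocol Appendix A, on the check immediately before dosing, names the 6-hour limit and no peri-operative limit.

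**Step 6. Analysis sets.**
- Undosed after randomisation: the patient stays in ITT (Protocol 7.3 and 12.6.2) but leaves mITT. Under Protocol 12.6.2 mITT requires exposure and is the primary effectiveness set.
- Dosed under inclusion 6: the patient stays in mITT but is at odds with Visit 2. Protocol 12.6.2 and SAP 2.3 allow PP exclusion for post-randomisation violations that could confound the effect.
- Never randomised because the site reads Visit 2 strictly: no analysis set is affected, but the enrolled population changes.

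**Step 7. Size, by assumption only.** The number of randomised but undosed patients is not given. Protocol 12.5.2 plans n = 60 per arm, 75% against 50%, one-sided 0.025. The normal approximation with pooled variance under the null is

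power = Φ{[0.25√n − 1.96√(2 × 0.625 × 0.375)] / √(0.75 × 0.25 + 0.50 × 0.50)}.

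At n = 60 this gives 81.6%, the protocol's figure. If an assumed share of each arm were undosed and so left mITT:

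| Assumed share undosed | n per arm | Power |
|---|---|---|
| 5% | 57 | 79.5% |
| 10% | 54 | 77.3% |
| 20% | 48 | 72.2% |

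Nothing in the documents makes any of these shares likely. The table shows only how the result would scale.

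**The case against.** The best defence is that the sentence was meant only to rule out dosing before surgery. It follows directly on the abdominal rule, it drops the pre-operative option, and its own parenthesis points to surgical confirmation. Nearly all the other dosing text is AKI-linked, including the list and Note just below it, and SAP 7.6 tabulates dosing as during or after surgery without the word *immediately*. A site reading the whole page might well dose these patients.

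As an account of intent this is plausible. It does not cure the wording. The NSTI item in the same list already forbids dosing before surgical confirmation, so the sentence is either redundant or adds a peri-operative limit, and its restrictive phrasing says the latter.

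Other parts of the defence stand and limit the point:
- *Immediately* is undefined, so AKI confirmed soon after surgery may qualify.
- A repeat debridement is surgery, including after transfer, so the bar is not absolute.
- A site reading Visit 2 strictly would more probably not randomise than randomise and withhold, because allocation follows AKI confirmation and the full criteria are checked before drug preparation.
- The PP set is optional and its exclusions are decided on blinded data. Dosing in line with inclusion 6 may well not be excluded.

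**Conclusion.** The inconsistency is real. One sentence conflicts with inclusion 5 and 6, the 48-hour follow-up and allocation trigger, the list and Note beside it, Protocol 8.1 and 9.2.1, and SAP 7.6. It concerns NSTI patients whose AKI is confirmed well after surgery and those operated on before transfer, apart from any who have a repeat operation in the window. The number affected is unknown.

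A reader might infer more than the documents support:
- *That late-AKI NSTI patients cannot be dosed under the protocol.* That is true of the one sentence. The other rules permit dosing.
- *That all such patients, and every transferred patient, are barred.* The undefined word and repeat surgery leave exceptions.
- *That a delayed-NSTI stratum is lost.* There is no such stratum. The strata are AKI acuity by age within site, and the delayed-AKI level also holds abdominal patients, who are unaffected.
- *That power or the mITT and PP sets will suffer.* Those losses depend on how sites act and cannot be sized from the documents.

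The matter should be corrected because it governs who receives study drug and is cheap to settle. It is a conflict of wording, not a flaw in the design.

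**What to change.** The sponsor should reconcile the Visit 2 sentence with inclusion 5 and 6, the Screening follow-up and allocation trigger, the Visit 2 list and Note, Protocol 8.1 and 9.2.1, and SAP 7.6. One statement should then govern when an NSTI patient whose AKI arises after surgery, or who was operated on before transfer, may be dosed. If any limit relative to surgery is kept, its terms need a definition, including whether repeat operations count.

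The acuity stratum (Protocol 4.5 and 12.6.1) and the 24-hour and 25–48-hour subgroup (Protocol 12.7, SAP 5.6 and 8.8) should then describe only patients whom the agreed rule allows to be dosed. This review takes no view on which timing rule is right.

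The cost is a short protocol clarification, taken through the approval route in Protocol 15.3.1, a memo to sites, and matching SAP wording. No extra data or patients are needed.

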6.3.1 Criteria for Premature Discontinuation from Study

In rare instances, the patient (or Investigator) may determine that he/she is not able to make all visits required by the protocol. Possible reasons for discontinuation from the study may include:

- Withdrawal of consent
- Lost to follow-up
- Other reasons such as administrative reasons

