- Concomitant medications
- Critical care parameters (dates and times of assisted ventilation, vasopressor use, ICU /hospital stay)
- Collect blood for systemic inflammatory biomarkers - leukocyte transcriptome (RNA expression) profiling and chemokine / cytokines at 72±4 hours post study drug administration – optional sub-study (Day 4 only)
- Record survival

Visit 5 (Day 7 [±1 day])

- Fluid balance (total I/O) for calendar day
- Detailed urine output
 - Should be recorded continuously from time of study drug administration to Day 7 (if still in ICU or step down unit (or equivalent), using most frequent hourly intervals available and by calendar day with or without Foley catheter in place
- Collect data on additional amputations if NSTI
- Collect data on acute RRT
- Record additional relevant procedures related to the kidney (e.g., renal biopsy)
- Record any imaging that evaluates the kidney
- Weight (if easily obtained)
- Collection of AEs/ SAEs including secondary infections
- Record any follow-up surgical or interventional radiologic procedures for previously documented abdominal infection or NSTI
- Concomitant medications
- Vital signs (to be taken during the morning tests)
- PE (visiting nursing service does not perform if outpatient)
- Standard CRP
- Spot urine for albumin to creatinine ratio
- Safety laboratory tests
 - Full chemistry panel (see Section 9.2.11)
 - CBC with differential and platelet count
- Critical care parameters (dates and times of assisted ventilation, vasopressor use, ICU /hospital stay)
- Record any hospital re-admissions (if previously discharged for original sepsis-related hospitalization)

- Systemic response: collect data for SOFA parameters
 - All efforts should be made to obtain the actual measurements of SOFA parameters at these visits-may use SpO2 value (and record FiO2) if arterial blood gas is not clinically indicated.
 - Platelet count, creatinine and total bilirubin values required for SOFA components can be obtained from safety laboratories performed at this visit.
- Assess lesion status if NSTI (healing/progression/significant change in appearance) if accessible for visible assessment at time of debridement or routine dressing change
- Collect urine and blood for plasma for storage (AKI biomarker analysis) – optional sub-study
- Record Survival

Visit 6 (Day 10 [±1 day]; perform only if patient is still hospitalized)

- Concomitant medications
- Collection of AEs/SAEs, including secondary infections

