Patients who received the study drug are required to complete the procedures outlined for this clinical study. Exceptions would only include the withdrawal of consent, lost to follow-up or death.

If a patient misses a scheduled visit, attempts to complete the patient data will be made via telephone or rescheduling the visit. After waiting one week for the response, a return-receipt, certified letter containing instructions to call for an appointment will be sent. If no response is obtained within one week after sending the return-receipt letter, the patient should then be considered as lost to follow-up. The returned receipt should be filed in the

Investigator's regulatory binder to document the site's attempt to arrange patient follow-up. A clinical evaluation should be made based on the last contact with the patient.

SAEs occurring within 28 days of a patient receiving IMP will be recorded and processed as described in Section 11.3 of the protocol.

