2.1.2 Sample Size Justification

This trial will enroll 120 subjects randomized in a 1:1 ratio to either Reltecimod 0.5 mg/kg (n=60) or placebo (n=60), both in addition to standard of care (SoC). Sample size analysis was performed assuming all patients will be evaluable for the primary endpoint due to using last observation carried forward (LOCF) for patients missing the creatinine value on Day 28. The primary efficacy hypothesis will be tested using an unadjusted χ^2 statistic with a one-sided $\alpha=0.05$ significance level. Rejection of the null hypothesis will only occur if investigational drug superiority is demonstrated. Statistical power was computed for a range of expected treatment group differences supported by the results of preliminary studies. The following table summarizes the statistical power for a total sample size of N=120 (60 per group) for various assumptions regarding the success rate in the investigational arm and assuming a success probability of 0.50 among controls. This sample size results in 89% power if the true success rates are 75% and 50% for the investigational drug and placebo, respectively, for a group difference of 25%. Power remains above 80% if the true group difference is at least 22% (Table 1).

Table 1. Computed Power			
Index	Control	AB103	Power
1	0.5	0.65	0.507
2	0.5	0.70	0.727
3	0.5	0.71	0.766
4	0.5	0.72	0.802
5	0.5	0.73	0.834
6	0.5	0.74	0.864
7	0.5	0.75	0.890

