5.11.2 LOCF of Day 28 and Day 90 Creatinine

In order to determine the primary endpoint, freedom from durable loss of eGFR at Day 28, creatinine is necessary. Patients surviving to Day 28 or later but with missing Day 28 creatinine will have their Day 28 creatinine values determined through LOCF. The same procedure will be used for Day 90 Creatinine.

5.11.3 mSOFA Scores

mSOFA scores over time will be assessed as 1) observed cases, and 2) LOCF.

⁶ Cohen, J. (1988). *Statistical power analysis for the behavioral sciences* (2nd ed.). New York, Academic Press.

⁷ Kaplan EL and Meier P. Nonparametric estimation from incomplete observations, *Journal of the American Statistical Association*, **53**:457-481, 1959

⁸ Knickerbocker R. Intent-to-Treat Analyses. In: Chow S-C, ed. *Encyclopedia of Biopharmaceutical Statistics*. Marcel Dekker; 2000.

Individually missing mSOFA component values due to non-measurement are conventionally assumed as normal and this convention will be followed for this study.

LOCF will not be applied to missing mSOFA scores after patient death in analyses that employ LOCF to describe mean values of time. Therefore, analysis of mSOFA mean values using LOCF will focus on morbidity rather than mortality. Also, LOCF will not be used for missing mSOFA after Day 14.

In categorical analyses including formulation of the secondary effectiveness endpoint, total mSOFA score at Day 14 ≤ 1 , LOCF is necessary to guarantee that every patient has a value at Day 14. LOCF will not be performed after patient death.

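### Protocol 7.3 lets a site class an unresponsive outpatient as lost before or as the primary Day 29 visit opens, and no text says contact must be re-attempted

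*Protocol*

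**What the plan says.** The contact procedure is in Protocol 7.3, under Follow-up of Patients. Its trigger is general: "If a patient misses a scheduled visit, attempts to complete the patient data will be made via telephone or rescheduling the visit." The next step is: "After waiting one week for the response, a return-receipt, certified letter containing instructions to call for an appointment will be sent." The last step is: "If no response is obtained within one week after sending the return-receipt letter, the patient should then be considered as lost to follow-up." A clinical evaluation is then to be based on the last contact. The same section requires dosed patients to complete the study procedures, with this qualification: "Exceptions would only include the withdrawal of consent, lost to follow-up or death."

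Other texts point the other way:

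- The Visit 9 text in 7.3 asks for every effort to obtain the data because Day 28 is the primary endpoint, with telephone follow-up as a fallback.
- Protocol 6.3 asks for end-of-study assessments whenever possible, has the site contact patients who fail to return for final assessments, and asks for every effort to obtain clinical outcome.
- Protocol 11.1 says survival is determined through 90 days, with no exception for lost patients.
- The opening of 7.3 contracts homecare visits from Day 7 through Day 90.

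On the analysis side, SAP 2.1.2 sizes the trial "assuming all patients will be evaluable for the primary endpoint", relying on last observation carried forward (LOCF). SAP 5.11.2 limits that method to known survivors: "Patients surviving to Day 28 or later but with missing Day 28 creatinine will have their Day 28 creatinine values determined through LOCF." SAP 3.10.6 and 3.10.7 apply LOCF to a missing Day 28 creatinine without that condition, and 3.10.6 takes values from Day 7 on.

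**The concern.** The primary endpoint needs three facts at Day 28: alive, free of dialysis, and less than a 37% loss of eGFR. A rule that lets follow-up lapse because of an interim visit can leave all three unknown, although that visit does not define the endpoint. The patients exposed are those discharged early enough to have outpatient visits at Day 7 or Day 14. Their prognosis may differ from that of patients still in hospital, so the missing outcomes need not be missing at random.

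The Day 90 data are exposed in the same way. SAP 4.2 lists freedom from durable loss and survival at Day 90 as secondary endpoints; the protocol treats Day 90 as exploratory.

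**Working it through.** The plan states neither a loss rate nor the day on which lost status would fall, so there is no figure to reproduce. The check is calendar arithmetic followed by a comparison of the texts.

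**Inputs (Protocol 7.3).** Visit windows: Visit 5, Days 6 to 8; Visit 7, Days 13 to 15; Visit 8, Days 20 to 22; Visit 9, Days 29 to 32; Visit 11, Days 90 to 95. Visit 6 (Day 10) applies only to patients still in hospital and is left out. Waits: 7 days for a response, then 7 days after the letter.

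**Formula.** Earliest lost day L = M + 7 + 7, where M is the day the visit counts as missed. The protocol does not define M, so three values are used: the nominal day, the last day of the window, and the day after the window closes. L is a minimum, because the first week runs from the contact attempt and the second from sending the letter.

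| Visit missed | M | L | Position |
|---|---|---|---|
| Day 7 | 7 / 8 / 9 | 21 / 22 / 23 | 8 / 7 / 6 days before Visit 9 opens |
| Day 14 | 14 / 15 / 16 | 28 / 29 / 30 | 1 day before / on / 1 day after Visit 9 opens |
| Day 21 | 21 / 22 / 23 | 35 / 36 / 37 | after the Visit 9 window closes (Day 32) |
| Visit 9 | 29 / 32 / 33 | 43 / 46 / 47 | 47 / 44 / 43 days before Day 90 |

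**What else happens in that time.** A patient lost from Day 7 has also passed the Day 14 window and has reached or passed the Day 21 window. A patient lost from Day 14 has passed the Day 21 window. Attending any of those visits would presumably count as a response.

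**Which text governs.** The Follow-up of Patients text removes the duty to complete procedures once a patient is lost. The Visit 9 text, 6.3 and 11.1 keep asking for data. None of them mentions a patient already classed as lost, and none says the status can be reversed or that contact resumes at Visit 9. A site that stopped at Day 21 and a site that kept calling could each cite the protocol.

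**How such a patient is scored.**

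- Missed Day 14 but seen at Day 7: SAP 3.10.6 allows the Day 7 creatinine to be carried to Day 28. SAP 5.11.2 does so only if the patient is known to have survived to Day 28. Vital and dialysis status are unknown, so the two sections can give different answers. Under 3.10.6 read alone, a favourable Day 7 value could produce a success if no recorded death or dialysis is taken to mean alive and dialysis-free.
- Missed Day 7 and silent since: there may be no value from Day 7 on to carry, and no rule says how the patient is scored.

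**Size per patient.** With 60 per arm, each patient scored wrongly moves that arm's success rate by 1/60 = 1.7 percentage points.

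**The case against.** The strongest reply is that the rule catches only patients who have been silent for at least two weeks, and that other sections already tell the site to keep trying. Both parts are largely right, and they limit the point in four ways.

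- A reader might infer that one missed Day 7 or Day 14 visit makes a patient lost. It does not. Lost status also requires no response to telephone or rescheduling, and then none to a certified letter.
- A reader might infer that the protocol orders follow-up to end. It does not. It lists lost patients as an exception to required procedures, while 6.3, 11.1 and the Visit 9 text still ask for data. The fault is a conflict left unreconciled.
- A reader might take 6.3.1 to make inability to attend a ground for discontinuation, since it says "the patient (or Investigator) may determine that he/she is not able to make all visits required by the protocol". Those words are introductory and limited to rare instances. The listed reasons are withdrawal of consent, loss to follow-up, and other reasons such as administrative ones.
- Early discharge may be uncommon in patients admitted to intensive or step-down care with Stage 2 or 3 kidney injury. The documents do not give its frequency.

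It is also fair to say that the missing scoring rule for unknown vital status would exist whatever the contact clock. It belongs here because the clock is one route by which such patients arise.

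What stands is that a written rule can close out a silent patient before or as the primary visit opens, and that no text overrides it.

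**Conclusion.** The concern holds in limited form. An outpatient who misses Day 7 or Day 14 and answers nothing can be classed as lost at about Day 21 to 23 or Day 28 to 30, against a Visit 9 window of Days 29 to 32. A silent patient who misses Visit 9 can be classed as lost at about Day 43 to 47. This assumes the two one-week waits run without delay; any delay moves the dates later. The conflict with 6.3, 11.1 and the Visit 9 text is real, and the SAP sections on a missing Day 28 creatinine do not agree on a patient whose survival is unknown.

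The number affected cannot be computed. A reader might apply a general loss rate, say 3% to 10% of 120 (about 4 to 12 patients), but the documents give no such rate. It would also count every loss, when the relevant patients are those who would have been reached at Visit 9 but for the classification.

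A reader might also note that, with 30/60 placebo successes, 41/60 gives one-sided p = 0.0205 and 40/60 gives p = 0.032, on either side of the protocol's 0.025. That is true of any binary endpoint in a trial this size and does not measure this rule. The SAP, which prevails over the protocol, tests at one-sided 0.05, where both results succeed.

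**What to change.** **Protocol 7.3.** State that a missed interim visit is recorded as missed only. State that contact is re-attempted at each later visit by homecare, telephone, or records where consent allows. State that lost status is not assigned for Day 28 before the Visit 9 window closes, nor for Day 90 before the Day 90 window closes. Reconcile this wording with 6.3, 6.3.1 and the Visit 9 text, so that a site knows which instruction applies to a silent patient.

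**SAP 3.10.6, 3.10.7 and 5.11.2.** Give one rule under which a carried-forward creatinine cannot by itself make a patient with unknown Day 28 vital status a success. One option is to score such a patient as not achieving the endpoint and to add a sensitivity analysis under other assumptions.

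**Cost.** A few protocol sentences, a short SAP edit and some extra contact attempts; the homecare vendor is already contracted to Day 90. The downside is that a few patients with unknown status would count as failures, some of whom may in fact have done well.
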